### CSF Substudy

Participation in the CSF substudy is voluntary. It is estimated that approximately 30% of subjects will participate in the CSF substudy. If the dropout rate in the CSF substudy is 12%, 20%, or 50%, then the number of subjects having final CSF assessment would be approximately 48, 44, or 27, respectively. The estimated standard deviation of percent change from baseline of cGMP concentrations after 9 weeks of treatment from pooled subjects in the CSF substudy is approximately 130%. The width of the 95% CI of the mean difference of percent change from baseline of cGMP concentrations after 9 weeks of treatment between E2027 and placebo for the 3 different sample sizes above would be approximately 74%, 77%, or 96%, respectively. Since mean percent change from baseline of cGMP concentrations after 9 weeks of treatment in the E2027 and placebo groups are expected to be approximately 200% and 5%, respectively, the sample size of the CSF substudy would be adequate to detect the mean difference of percent change from baseline of cGMP concentrations after 9 weeks of treatment between E2027 and placebo groups.

## **5 STATISTICAL METHODS**

All statistical tests will be 2-sided at the 5% significance level unless otherwise stated. All descriptive statistics for continuous variables will be reported using mean, standard deviation (SD), median, minimum, maximum and number of subjects with non-missing data. Categorical variables will be summarized as number (percentage) of subjects.

### **5.1 Study Endpoints**

The details of calculating each efficacy endpoint are presented in Section 8.3 ALGORITHMS FOR EFFICACY PARAMETERS. The details of calculating each QoL endpoint are presented in Section 5.7 OTHER ANALYSES.

#### **5.1.1 Primary Endpoints**

Change from baseline in the MoCA total score at 12 weeks of treatment

CIBIC-Plus scale at 12 weeks of treatment

#### **5.1.2 Secondary Endpoints**

CGIC-DLB scale at 12 weeks of treatment

- Change from baseline at 12 weeks of treatment in the following endpoints:

- CFI score
- MMSE total score
- NPI total score, subscores and caregiver or informant distress score

Safety and tolerability of E2027 as measured by

- Incidence of adverse events including severe AEs, serious AEs, AEs resulting in discontinuation
- Incidence of orthostatic hypotension and orthostatic tachycardia
- Incidence of markedly abnormal laboratory values and shifts from baseline of laboratory values
- Incidence of abnormal ECG parameters and abnormal ECG findings
- Incidence of suicidality based on C-SSRS
- Changes from baseline in the total score of UPDRS-III

### 5.1.3 Exploratory Endpoint(s)

- Change from baseline at 12 weeks of treatment in the following endpoints:
  - SCOPA-Sleep total score and subscores
- Change from baseline at 12 weeks of treatment in the following endpoints:
  - Total score and domain scores of the DEMQOL and DEMQOL-Proxy
  - EQ-5D utility score and EQ-5D health status rating
- Percentage change from baseline in CSF cGMP concentrations after 9 weeks of treatment
- CIBIC-plus sub-items (Attention, Orientation, Memory, etc) rating

## 5.2 Study Subjects

### 5.2.1 Definitions of Analysis Sets

The Randomized Set is the group of subjects who are randomized to study treatment.

The Safety Analysis Set is the group of subjects who receive at least 1 dose of study drug and have at least 1 post dose safety assessment. The Safety Analysis Set will be used in the statistical analyses for safety. In the event that a subject received study drug different from the one to which this subject was randomized, the subject's safety data will be analyzed "as actually treated" for the safety analyses.

The Full Analysis Set (FAS) is the group of randomized subjects who receive at least 1 dose of study drug and have baseline and at least 1 post dose primary efficacy measurement. In the event that a subject received study drug different from the one to which this subject was

randomized, the subject's efficacy data will be analyzed "as randomized" for the FAS analyses.

The PK Analysis Set is the group of subjects with at least 1 quantifiable E2027 serum concentration with a documented dosing history.

The PD Analysis Set is the group of subjects who have sufficient PD data to derive at least 1 PD parameter.

The Per Protocol (PP) Analysis Set is the subset of subjects in the Full Analysis Set who sufficiently complied with the protocol. It may include subjects who complete certain pre-specified minimal exposure to the treatment and have no major protocol violations such as wrong diagnosis, error in treatment assignment, use of prohibited medication and poor compliance. The precise reasons for excluding subjects from the Per Protocol Set will be fully defined and documented before database lock, see Section 5.2.3.

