9.7.1.2 Definitions of Analysis Sets

- The Randomized Set is the group of subjects who are randomized to study drug
- The Safety Analysis Set is the group of subjects who receive at least 1 dose of study drug and have at least 1 postrandomization safety assessment
- The Full Analysis Set (FAS) is the group of randomized subjects who receive at least 1 dose of study drug and have baseline and at least 1 postrandomization coprimary efficacy measurement
- The Per Protocol Analysis Set (PPS) is the subset of subjects in the Full Analysis Set who sufficiently complied with the protocol. It may include subjects who complete certain pre-specified minimal exposure to the treatment and have no major protocol violations such as wrong diagnosis, error in treatment assignment, use of inhibited medication and poor compliance. The precise reasons for excluding subjects from the PPS will be fully defined and documented before database lock.
- The PK Analysis Set is the group of subjects with at least 1 quantifiable plasma E2027 concentration with a documented dosing history
- The PD Analysis Set is the group of subjects who have sufficient PD data to derive at least 1 PD parameter
- The PK/PD Analysis Set is a group of subjects with at least 1 quantifiable plasma E2027 concentration, except for placebo subjects, and at least 1 PD measurement with a documented dosing history.

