9.7.1.6 Efficacy Analyses

The significance level for all efficacy endpoint analyses is 0.05 (2-sided), unless otherwise stated, with no adjustments for multiplicity. The efficacy analyses will be performed on the FAS except per protocol analysis will be performed on the PPS.

Baseline for the primary and secondary efficacy endpoints is defined as the last pretreatment assessment. An additional baseline, based on the mean of all prerandomization values at the Screening and Baseline assessment, will be explored due to assess potential prerandomization variability.

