In order to generate inputs for proposed primary and sensitivity analyses, a MMRM will be used for the E2027 group completers, placebo group completers, and all placebo group subjects. The model will be adjusted for baseline MoCA, visit (Weeks 6 and 12), randomization stratification variable (receiving AChEI or not; geographical region [North America, Europe, Japan]), and baseline MoCA × visit as fixed effects. An unstructured covariance matrix will be used to model the covariance of within subject effect. The values of baseline MoCA will be adjusted using the overall baseline mean of all study subjects in computing LS-means.

The primary analysis of CIBIC-Plus scale at 12 weeks will be based on control-based pattern imputation at subject level ([Yuan 2014](#)). The CIBIC-Plus scale at 12 weeks will be imputed as an ordinal response variable. The same missing reasons and corresponding missing mechanism as in the analysis of change from baseline in MoCA total score will be used in this analysis. Only the missing ordinal responses in E2027 treatment group considered as MNAR will be imputed by ordinal responses observed in the placebo group using a pattern-mixture model approach under MNAR assumption. Other missing ordinal responses will be imputed assuming MAR. The CIBIC-Plus scale at 12 weeks (observed or imputed) will be analysed using proportional odds model, a special case of generalized linear mixed models (GLMM), in multiply imputed data sets. The results obtained from all multiply imputed data sets will be combined for overall inference using Rubin's rules. The GLMM model will include treatment, randomization stratification variables (receiving AChEI or not; geographical region [North America, Europe, Japan]) as fixed effects. The model will be fitted using GLMM with a multinomial distribution and a cumulative logit link function. The proportional odds ratio estimate between E2027 and placebo, the corresponding 95% CI, and *P*-values will be presented.

The sensitivity analysis for CIBIC-Plus scale will be a tipping point analysis based on multiple imputation at subject level using pattern mixture model approach ([Yuan, 2014](#)), which is based on an increasingly more conservative shift parameter (based on cumulative logit function values for CIBIC-Plus scale) such that the *P*-value is equal to the pre-specified alpha (0.05 [2-sided]). Additional sensitivity analysis for different classification of missing

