## 5.4 Efficacy Analyses

### 5.4.1 Primary Efficacy Analyses

The treatment effect of interest will be the efficacy as measured by co-primary endpoints that would be observed at 12 weeks regardless of whether or when the assigned treatment was discontinued due to adverse event, lack of efficacy or any other events related to treatment or

study outcome. The target population is DLB subjects defined by inclusion/exclusion criteria.

There are 2 co-primary efficacy endpoints, change from baseline in the MoCA total score at 12 weeks and CIBIC-Plus scale at 12 weeks. Overall there are 2 null hypotheses ( $H_0$ ) to be tested in the primary analysis:

$H_{01}$ : There is no difference in the mean change from baseline in the MoCA total score at 12 weeks between E2027 and placebo.

$H_{02}$ : The proportional odds ratio based on CIBIC-Plus scale at 12 weeks between E2027 and placebo is equal to 1.

The corresponding 2 alternative hypotheses are that there is a difference in the mean change from baseline in MoCA total score at 12 weeks in this co-primary endpoint between E2027 and placebo and the proportional odds ratio based on CIBIC-Plus scale at 12 weeks between E2027 and placebo is not equal to 1. The study will be considered positive if statistically significant improvement (at level of 0.05 (2-sided) or 0.025 (1-sided)) is observed in both co-primary endpoints in E2027.

Due to correspondence with the FDA during the study, separate analyses will be performed for the non-EMA and EMA registrations, the endpoints remain identical.

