The missing endpoint values considered as MAR can be imputed using condition distribution from the observed endpoint values and therefore can be handled by MMRM analysis assuming MAR. The mean of missing endpoint values in the E2027 treatment group considered as MAR can be viewed as implicitly imputed using the estimated means of endpoint values of completers and all subjects through MMRM analysis including completers and subjects with missing values considered as MAR in the E2027 treatment group. The mean of missing endpoint values in E2027 treatment group considered as MNAR will be imputed by the mean of the overall endpoint distribution under placebo as described next. The mean of the overall endpoint distribution under placebo will be obtained using mixed effects model of repeated measures (MMRM) within placebo group assuming MAR. Test statistics and the p-value will be obtained as described by Mehrotra, et al. (2017). In the presence of subjects with missing endpoint values considered as MAR, the superscript of “drop” refers to “subjects with missing endpoint values considered as MNAR” and the superscript of “comp” refers to “completers and subjects with missing endpoint values considered as MAR”.

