### **Sensitivity Analysis of Change from Baseline in the MoCA Total Score at 12 Weeks for EMA registration**

A sensitivity analysis will be produced to repeat the primary analysis for MoCA but to censor data after changes in AChEI medications. For this the following missing mechanism will be added to the above reasons in the primary analysis

The effect had rescue medication not been made available to subjects prior to week 12 is not observable for subjects who initiated prohibited or restricted rescue medication. For these subjects, the data collected after initiation of prohibited rescue medication are assumed to contain no treatment effect in the E2027 treatment group. Technically, response data collected after initiation of new AChEIs or after any change in concomitant AChEIs stable dose will be treated as MNAR such that response data treated as MNAR in the E2027 treatment group would be imputed by the mean response in the placebo treatment group as described by the imputation method below.

In order to generate inputs for proposed primary and sensitivity analyses for the EMA registration, a MMRM will be used in separate MMRM analyses for each treatment group for all randomized subjects as well as completers assuming MAR for both treatment groups. The model will be adjusted for baseline MoCA, visit (Week 6 and Week 12), randomization stratification variables (receiving AChEI or not, geographical region [North America, Europe, Japan]), and baseline MoCA  $\times$  visit as fixed effects. An unstructured covariance matrix will be used to model the covariance of within subject effect; if MMRM fails to converge then a covariance structure with fewer parameters from the following list will be employed according to the prespecified order in the list until the MMRM converges. The list of covariance structure will include Heterogeneous Toeplitz, Toeplitz, Heterogeneous

Compound Symmetry, and Compound Symmetry. The Kenward-Roger approximation will be used to estimate the denominator degrees of freedom when unstructured covariance matrix is used. If MMRM fails to converge and a structured covariance matrix is used, the empirical method will be used to compute variance-covariance matrix of the fixed-effects parameters (sandwich estimator). The values of baseline MoCA will be adjusted using the overall baseline mean of all study subjects in computing least square (LS)-means.

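### The plan does not settle which subjects enter the EMA control-based analyses; if the FAS governs, E2027 MNAR dropouts with no post-dose score are left out of the placebo-based imputation

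*SAP*

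**What the plan says.** **Analysis set.** SAP 5.2.1 limits the FAS to dosed subjects who "have baseline and at least 1 post dose primary efficacy measurement". Protocol 9.7.1.2 has the same restriction: they must "have baseline and at least 1 postrandomization coprimary efficacy measurement". Protocol 9.7.1.6 then states: "The efficacy analyses will be performed on the FAS except per protocol analysis will be performed on the PPS". SAP 5.4.1 names no set for the main co-primary analyses; only the per-protocol repeat has one.

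**EMA input models.** The SAP's EMA text for MoCA calls for "separate MMRM analyses for each treatment group for all randomized subjects as well as completers assuming MAR for both treatment groups". The protocol synopsis has the same population. Protocol 9.7.1.6.1 differs: "a MMRM will be used for the E2027 group completers, placebo group completers, and all placebo group subjects".

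**Treatment effect of interest and imputation.** SAP 5.4.1 targets the efficacy that "would be observed at 12 weeks regardless of whether or when the assigned treatment was discontinued due to adverse event, lack of efficacy" or other treatment-related events. For MoCA in the EMA analysis, "missing endpoint values in E2027 treatment group considered as MNAR will be imputed by the mean of the overall endpoint distribution under placebo". For CIBIC-Plus, E2027 dropouts classed as MNAR are imputed subject by subject from placebo data. CFI and NPI follow the MoCA method, CGIC-DLB follows CIBIC-Plus, and MMSE uses ANCOVA with control-based imputation (SAP 5.4.2).

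**When scores are collected.** The scheduled post-dose efficacy visits in the treatment period are Weeks 6 and 12. MoCA and CIBIC-Plus are also listed for the ED and Unscheduled Visits (protocol Table 6). Subjects who stop drug are expected to keep attending scheduled visits (SAP 3.2). Post-ED data enter all analyses (SAP 5.3.5.1), and Days 1 to 63 map to Week 6 (SAP 8.1.2).

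**The concern.** The EMA rule for an E2027 subject who leaves for an MNAR reason needs only a classification. It does not need a post-dose score, because the value assigned comes from placebo. An analysis set that requires a post-dose score therefore works against the rule: it can remove subjects whom the rule exists to cover. Whether a subject has a score is settled after randomization and may depend on treatment.

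For MoCA, CFI and NPI such a subject drops out of the MNAR fraction, and the estimate moves away from the placebo mean. For CIBIC-Plus, CGIC-DLB and MMSE the subject is never imputed. Nothing on the placebo side offsets this, because the placebo mean comes from an MMRM under MAR, to which a subject with no score adds nothing.

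As the text stands, two programmers could use different denominators for a registration analysis. No listed analysis would show the difference. The tipping-point and all-missing-as-MNAR analyses in protocol 9.7.1.6.1 do not appear in SAP Table 4. SAP 5.2.3 tabulates exclusions from the per-protocol set by reason and arm, but no such table is specified for the FAS.

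**Working it through.** **Inputs from SAP section 4.** 80 completers and 91 randomized per arm; 12% dropout; MoCA difference 0.6 (planned), or 1.4 with SD 3 (from blinded data).

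**Plan's own figure.** 80 / (1 − 0.12) = 90.9, so 91 per arm and 182 in total. This reproduces. The implied E2027 dropouts are 91 − 80 = 11.

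**Assumptions, not in the documents.** All 11 dropouts are MNAR; the difference in the remaining subjects is δ; x of the 11 have no post-dose MoCA or CIBIC-Plus at any visit.

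**Estimate.** With MNAR subjects set to the placebo mean, estimate = (1 − π) × δ, where π is the MNAR share of the E2027 analysis set. Keeping everyone gives π = 11/91. Dropping x gives π = (11 − x)/(91 − x).

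| x lost | π | Estimate, δ = 0.6 | Estimate, δ = 1.4 | Ratio |
|---|---|---|---|---|
| 0 | 12.1% | 0.528 | 1.231 | 1.000 |
| 2 | 10.1% | 0.539 | 1.258 | 1.022 |
| 4 | 8.0% | 0.552 | 1.287 | 1.046 |
| 8 | 3.6% | 0.578 | 1.349 | 1.096 |
| 11 | 0% | 0.600 | 1.400 | 1.138 |

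The ratio simplifies to 91/(91 − x), for example 91/89 = 1.022 and 91/80 = 1.138. It depends only on how many MNAR subjects are lost; the total of 11 only caps x. For x of 2 to 4 the shift is 0.012 to 0.024 points at δ = 0.6, and 0.03 to 0.06 points at δ = 1.4.

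**Test statistic (delta method).** Take δ = 1.4, SD 3 and 80 observed per arm. Then Var(δ̂) = 9 × 2/80 = 0.225, a standard error of 0.474. With n the size of the E2027 analysis set, Var(estimate) ≈ (1 − π)² × 0.225 + δ² × π(1 − π)/n.

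- x = 0: 0.1739 + 0.0023 = 0.1762; z = 1.231/0.4197 = 2.932
- x = 2: 0.1818 + 0.0020 = 0.1838; z = 1.258/0.4287 = 2.935
- x = 4: 0.1902 + 0.0017 = 0.1919; z = 1.287/0.4381 = 2.939

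Estimate and standard error scale together, so z hardly moves. At δ = 0 the estimate is zero whatever x is. This approximates the test in the cited methods article, which is not available here.

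**Not computed.** The effect on the CIBIC-Plus odds ratio depends on the category distribution, which the documents do not give. **Non-EMA MMRM.** A subject with no post-dose score contributes nothing to the fit, so the result is the same on either set.

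**The case against.** **The loss is conditional.** A reader might infer that the plan definitely excludes early E2027 dropouts. The documents do not show that. The link from the FAS to the efficacy analyses is in the protocol, not in SAP 5.4.1. If the SAP's all-randomized wording governs, these subjects are imputed. Moreover, that wording describes MMRM inputs, where a subject without a score changes nothing, and the SAP never states the denominator of the MNAR share. Within the SAP alone this is closer to a silence than a contradiction. This stands; the conflict appears when protocol and SAP are read together.

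**Few subjects may be affected.** This also stands. The ED Visit, Unscheduled Visits, continued attendance and the wide Week 6 window give several chances for a score, and one score on either co-primary appears to be enough for the FAS. Attendance is not assured, though. Protocol 9.5.5 foresees subjects who stop returning, and the SAP's EMA text foresees assessments missed through delirium, drowsiness or refusal.

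**Who they are is unknown.** It is tempting to assume that subjects with no score are mostly AE or lack-of-efficacy dropouts. The documents do not support this. The primary discontinuation reasons in protocol 9.5.5 include loss to follow-up, subject choice and withdrawal of consent, and do not list lack of efficacy. Some of these subjects would be classed as MAR and were never due the placebo mean; losing them has a small effect in the opposite direction.

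**The inference barely changes.** This stands for MoCA. It does not remove the mismatch between the estimate and the treatment effect that the SAP says it targets.

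**Conclusion.** The point holds in conditional form. Protocol and SAP leave the population of the EMA analyses unresolved. If the FAS governs, a stated rule removes E2027 subjects who are MNAR and have no MoCA or CIBIC-Plus at any visit, contrary to a treatment effect defined regardless of discontinuation.

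The effect on the MoCA point estimate runs from 0% to 14% over the full range of x. It is about 2% to 5% if 2 to 4 subjects lack a score, which is an assumed count. A 0.03 to 0.06 point shift at δ = 1.4 is small against a standard error near 0.47. A reader might infer an inflated false-positive risk or a threat to the study's main conclusion; the calculation supports neither. The matter is worth correcting because it bears on the EMA estimate and its denominator, and because the correction is cheap.

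**What to change.** 1. In SAP 5.4.1 and 5.4.2, name one set for the EMA analyses: all randomized subjects with at least one dose and a baseline, without the post-dose measurement condition. Use that set in place of the all-randomized wording for the input models.
2. Classify subjects with no post-dose score as MNAR or MAR by reason, under the existing EMA rules. Include them in the dropout fraction (MoCA, CFI, NPI) and in the control-based imputation (CIBIC-Plus, CGIC-DLB, MMSE). State the denominator of the MNAR share.
3. Reconcile protocol 9.7.1.2, 9.7.1.6 and 9.7.1.6.1 with SAP 5.2.1 and the EMA text, and record the change in SAP section 7.
4. Report by arm and reason the number of subjects with no post-dose efficacy score. This figure shows whether the point matters in practice.

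The cost is SAP wording and a matching protocol note, since the protocol defines the FAS too. The analysis gains a few more imputed values, and the EMA estimate becomes slightly smaller.

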## 5.2.2 Subject Disposition

The number of subjects screened, the number (percent) of subjects who failed screening, and the reasons for screen failure will be summarized, based on data reported on the Screening Disposition eCRF. The distribution of the number of randomized subjects by each site will be summarized by treatment group and total.

Study Completion: the number (percent) of randomized and treated subjects who completed the study and who discontinued from the study will be summarized according to the primary reason for discontinuation and secondary reason(s) for discontinuation, based on data reported on the Subject Disposition (Study Phase) CRF. The number (percent) will be presented by treatment group, overall and by stratification factors.

Completion of Study Treatment: the number (percent) of randomized and treated subjects who completed study treatment and who discontinued from study treatment will be summarized according to the primary reason for discontinuation and also according to secondary reason(s) for discontinuation, based on data reported on Early Discontinuation from Study Drug eCRF. The number (percent) will be presented by treatment group and total, overall and by stratification factors. Subjects who discontinued study treatment but were followed up for efficacy assessments after treatment discontinuation will also be summarized.

